9.3.4.3 Pharmacokinetics for Subcutaneous Dosing (Sub-Study)

Subjects must first meet the eligibility criteria listed in [Section 8.4.4](#) before participating in the subcutaneous PK sub-study. The Investigator ensures the subject has given and documented their consent to participate in the sub-study before performing related procedures.

As a result of the review of real-time, open-label LDL-C values, the sponsor informs the Investigator as to which subject(s) qualify for the sub-study. This determination is made following the subject's Day 15 visit and the subsequent reporting of the LDL-C level from the visit. The Investigator inquires of the subject's ability and continued consent to participate in the sub-study (Inclusion Criteria).

Eligible subjects that have consented to the sub-study will have resumed taking daily oral atorvastatin at their lead-in dose since Day 16. They then return to the study center on Day 22 \pm 2 days after being instructed by the Investigator to refrain from taking their daily oral dose of atorvastatin at home on the day of the visit.

Subjects receive a subcutaneous dose of atorvastatin injection ([Section 8.3.2.2](#)), then samples are drawn at the following times after the time of the SC dose; allowable windows are listed in [Table 9-3](#):

- 30 minutes
- 1 hour

- 2 hours
- 4 hours
- 6 hours
- 8 hours
- 24 hours

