9.3.6.3 Subcutaneous Dosing (Sub-Study)

Those subjects that are participating in the sub-study resume their Lead-in daily oral dose of atorvastatin beginning on Day 16. Their oral dose is withheld on the day of their Day 22 Visit while they return to the clinic for a subcutaneous injection given as close as possible to the time of day at which they take their oral dose. The dose amount administered is the same as that which was taken intravenously during the treatment period.

Subjects that are not participating in the sub-study resume their standard of care treatment, if any, for hypercholesterolemia while they await their Day 22 follow-up call.

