- To compare the PK profile of atorvastatin administered by the IV route to that of oral administration, the following parameters of atorvastatin, 2-hydroxy atorvastatin and 4-hydroxy atorvastatin will be calculated for each of the four final multiple dosing injectables (IV and SC) treatment cohorts:

- Maximum serum concentration (C_{max})
 - Area under the curve to infinity (AUC_{inf})
 - Area under the curve to 24 hours (AUC_{0-24})
 - Elimination half-life ($T_{1/2}$)
 - Volume of distribution at steady state (Vd_{ss})
 - Elimination rate constant (K_{el})
 - Clearance (CL)

- To explore the PK profile of a single dose of atorvastatin administered by the SC route, the following parameters of atorvastatin, 2-hydroxy atorvastatin and 4-hydroxy atorvastatin will be calculated for each of the three final treatment cohorts:

- C_{max}
 - AUC_{inf}
 - AUC_{0-24}
 - $T_{1/2}$
 - Vd_{ss}

- K_{el}
- Apparent clearance (CL/F)
- To assess the safety of the study drug, the following will be evaluated:
 - Adverse events
 - Mean change (baseline to Day 15) for creatine phosphokinase (CPK), alanine aminotransferase (ALT) and aspartate aminotransferase (AST) in each dosing cohort.

4 Study Design and Methods

This is a Phase II, open-label, single-center dose-ranging study.

Three treatment cohorts of 13 subjects each are planned for intravenous route of administration. The different cohorts are composed of subjects taking three of the four commercially-prescribed levels of daily oral dosing: 10, 20, and 40 mg. The 4th Cohort for 80 mg oral dosing did not proceed with enrollment (per Amendment 3). Instead a 4th Cohort of 10 subjects (Amendment 03 of the protocol (Sections 9.3.6.2.3 and 12.2)) following the daily oral dosing of 20 mg will receive 15 days of subcutaneous treatment with atorvastatin. Subjects are treated with daily doses of injectable atorvastatin intended to be non-inferior to the efficacy of their stable oral dose at baseline.

Enrollment of subjects into any one of the cohorts that does not prove to meet the primary endpoint is terminated as soon as this determination is made, and a new cohort intended for 13 subjects is opened at an adjusted dose with intentions to meet the primary endpoint (See Table 1).

Table 1: Treatment Assignment – Main Study

Cohort	Lead-in Daily Dose of Oral Atorvastatin	Initial Targeted, Daily IV or SC Atorvastatin Dose	Maximum Daily IV or SC Atorvastatin Dose, after Escalations	Subjects
1	10 mg	2 mg IV	5 mg IV	13

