4.1.2 Pharmacokinetic Measurements

The PK measurements in each dosing cohort are the assessments of plasma concentrations of atorvastatin and its metabolites (2-hydroxy atorvastatin and 4-hydroxy atorvastatin) in the oral administration and the administrations by the injectable route.

At the oral PK visit (Screening Period), serial PK blood samples to measure plasma concentrations of atorvastatin and its metabolites will be collected within 60 minutes prior to taking the oral dose of atorvastatin, at 30 minutes (\pm 5 minutes), 1, 2, 4, 6, and 8 h (\pm 10 minutes) after taking the oral dose.

Levels of atorvastatin and metabolites measured from the pre-dose (oral) timepoint are imputed as 24-hour levels since the subject is on daily, constant dosing.

In the last dose of injectable atorvastatin at Day 15 visit, serial PK blood samples to measure plasma concentrations of atorvastatin and its metabolites will be collected within 60 minutes prior to the start of the dose, immediately after completion of IV dose (within 3 to 7 minutes), at 30 minutes (\pm 5 minutes), 1, 2, 4, 6, and 8 h (\pm 10 minutes) after completing the injected dose.

Levels of atorvastatin and metabolites measured from the pre-dose (IV) timepoint are imputed as 24-hour levels since the subject is on daily, constant dosing.

In the sub-study for the single SC atorvastatin dose, serial PK blood samples to measure plasma concentrations of atorvastatin and its metabolites will be collected at 30 minutes (\pm 5 minutes), 1, 2, 4, 6, 8 (\pm 10 minutes) and 24 h (\pm 60 minutes) after the SC dose.

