5.7.2 Pharmacokinetic Parameters

Pharmacokinetic parameters will be derived for atorvastatin and its metabolites for subjects in the PK population.

Pharmacokinetic parameters are defined in Table 4.

Table 4: Pharmacokinetic Parameters

Parameter	Description
C_{\max}	Maximum plasma concentration
AUC_{0-24}	Area under the plasma concentration-time curve from time zero to 24 hours
AUC_{∞}	Area under the plasma concentration-time curve from time zero to infinity
T_{\max}	Time to reach maximum plasma concentration
$T_{1/2}$	Elimination half-life
K_{el}	Elimination rate constant
$Cl(/F)$	(Apparent) clearance of drug from plasma for extravascular dosing
VD_{ss}	Volume of distribution at steady state for intravenous dosing
V_z/F	Apparent volume of distribution for extravascular dosing

Pharmacokinetic parameters will be calculated using noncompartmental methods and actual blood sampling times. In case of missing actual time, planned (or nominal) time will be used.

Concentration listed as below the limit of quantitation will be set to zero for the calculations. If a sample is missing or the value is not reportable and is between two measurable concentrations, the value at that time point will be left blank for the analysis and reported as either Not Reportable (NR) or No Sample (NS).

The PK timepoint at 24-hour post oral dosing is the pre-dose concentration due to reaching steady state. The first timepoint immediately following IV bolus dosing is set as 0.0055 hour (assume 20 seconds bolus dosing). The 24-hour post-dose concentration is set as pre-dose concentration before IV and multiple-dose SC dosing. For the single dose SC (sub-study) the pre-dose concentration is the 24-hour post-oral dose concentration.

No value of K_{el} , AUC_{∞} or $t_{1/2}$ will be reported for cases that do not exhibit a terminal log-linear phase in the concentration versus time profile. If the adjusted R-squared value ($Rsq_{adjusted}$) is < 0.8 , the analyst may evaluate if other time points are more appropriate and use those for the calculation of K_{el} , or no value of K_{el} , AUC_{∞} or $t_{1/2}$ will be reported.

For determination of AUC_{∞} , if calculated AUC from last to infinity is greater than 20% of the calculated AUC from 0 to infinity, then AUC_{∞} will not be reported.

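### Single-dose SC profiles begin about 24 h after the last oral dose and are analysed without a carry-over correction, so SC exposure is overstated wherever the oral trough is quantifiable

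*SAP*

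**What the plan says.** Protocol 9.3.6.3 sets the run-up to the SC dose: "Those subjects that are participating in the sub-study resume their Lead-in daily oral dose of atorvastatin beginning on Day 16". On the sampling day, "Their oral dose is withheld on the day of their Day 22 Visit", and the injection is given as near as possible to the usual time of the oral dose. Protocol 9.3.4.3 confirms the oral restart: "Eligible subjects that have consented to the sub-study will have resumed taking daily oral atorvastatin at their lead-in dose since Day 16". The SC amount is tied to the IV amount: "The dose amount administered is the same as that which was taken intravenously during the treatment period".

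Sampling after the SC dose runs from 0.5 h to 24 h (Protocol 9.3.4.3 and Table 9-3; SAP 4.1.2). No pre-dose sample is scheduled on Day 22. SAP 5.7.2 fills the gap: "For the single dose SC (sub-study) the pre-dose concentration is the 24-hour post-oral dose concentration". The same section says where an oral 24-hour value comes from: "The PK timepoint at 24-hour post oral dosing is the pre-dose concentration due to reaching steady state". That is the pre-dose sample of the Lead-in End Visit.

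SAP section 3 lists the parameters wanted from the sub-study under the aim "To explore the PK profile of a single dose of atorvastatin administered by the SC route": Cmax, AUCinf, AUC0-24, T1/2, Vdss, Kel and CL/F, for parent and both metabolites. SAP 5.7.2 derives them by noncompartmental methods. Neither document gives a baseline subtraction, a residual-decay correction, an exclusion for a high starting level or a sensitivity analysis.

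**The concern.** A single-dose profile can be read as such only if no drug is present at time zero. Here the washout is one dosing interval after several daily oral doses, so any oral drug still measurable is added to the SC concentrations and attributed to the SC dose. Two features of the plan could enlarge the effect. First, the residual comes from a larger dose: the IV amount carried over to SC starts at 20% of the oral dose and may not exceed 50% of it (Protocol Table 9-4 and 9.3.6.2.2). Second, the metabolites are analysed too, and Protocol 5.4 says parent-to-metabolite ratios differ between oral and IV dosing, so the distortion may differ by analyte.

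At stake is the description of SC pharmacokinetics after one dose. This serves a stated objective. The sub-study is closed under Amendment 3, but its analysis remains in SAP version 2.0.

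**Working it through.** The plan states no figure on this point, so there is nothing to reproduce. The documents give no half-life, trough or quantification limit, so the sizes below rest on assumptions, marked as such.

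**Washout.** Oral doses on Days 16 to 21 make 6 doses, or 4 to 8 with the Day 22 ± 2 window. The last is about 24 h before the SC dose. After n daily doses the fraction of steady state is 1 − exp(−24nk), with k = ln 2 / half-life. For n = 4 and a 14 h half-life this is 1 − 2^(−96/14) = 0.99, so treating the oral level as steady state is fair.

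**Residual AUC.** Assume one-exponential decline and the same k for both routes. At steady state the oral concentration is A·exp(−kt)/(1 − r), with r = exp(−24k).
- Oral AUC over one interval: A/k.
- Residual oral AUC in the 24 h after the SC dose: A·r/k, that is, r times the oral interval AUC.
- If true SC AUC0-24 is ρ times the oral interval AUC, AUC0-24 is overstated by r/ρ. In this model AUCinf is inflated by the same fraction, and CL/F changes by −(r/ρ)/(1 + r/ρ).

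| Assumed half-life | r | AUC0-24, ρ = 1 | CL/F, ρ = 1 | AUC0-24, ρ = 0.5 | CL/F, ρ = 0.5 |
|---|---|---|---|---|---|
| 4 h | 0.016 | +2% | −2% | +3% | −3% |
| 7 h | 0.093 | +9% | −8% | +19% | −16% |
| 10 h | 0.189 | +19% | −16% | +38% | −27% |
| 14 h | 0.305 | +30% | −23% | +61% | −38% |

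Both values of ρ are assumed.

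**Cmax, and size in terms of the starting level.** A second calculation adds C0·exp(−kt) to a one-compartment SC curve (assumed absorption rate 1.5/h, half-lives 4 to 30 h). It uses the sub-study sampling times, the linear trapezoid rule and a terminal slope from the last three points.

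| C0 as share of SC-only Cmax | Cmax, AUC0-24, AUCinf | CL/F |
|---|---|---|
| 0% | none | none |
| 1% | +0.7% to +0.9% | −0.7% to −0.9% |
| 5% | +3.5% to +4.7% | −3.6% to −4.4% |
| 10% | +7% to +9.5% | −7% to −8.5% |
| 20% | +14% to +19% | −13% to −16% |

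**Contribution of the time-zero rule.** Setting time zero to 0 instead of C0 changes only the first trapezoid, by 0.5 × C0 / 2 = 0.25·C0. The whole residual AUC is C0(1 − r)/k: 5.7·C0 at a 4 h half-life and 14·C0 at 14 h. The rule therefore carries 0.25/5.7 = 4% down to 0.25/14 = 2% of the residual. The rest lies in the measured post-dose concentrations.

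**Effect of the existing rules.** SAP 5.7.2 withholds AUCinf when more than 20% is extrapolated. In the second calculation the extrapolated share is 2% at a 4 h half-life, 13% (12% at the higher starting levels) at 8 h and 25% at 12 h. At 12 h and above, AUCinf and any CL/F based on it would drop out; Cmax and AUC0-24 would still be reported with the residual included.

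**The case against.** The strongest reply is that the bias is conditional. If the oral 24-hour level is below quantification, SAP 5.7 and 5.7.2 set it to zero and carry-over is negligible. This stands: a reader might infer that single-dose SC exposure is certainly overstated, and the documents do not support that.

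A reader might also infer that the quoted rule creates the bias. It does not. A non-zero start describes the subject's state correctly, and the rule accounts for only about 2% to 4% of the residual AUC. The cause is the short washout together with the missing correction.

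The percentages are illustrative. If the ratio of 0.5 is read as SC AUCinf to oral interval AUC, the 14 h case becomes 0.305/(0.5 × 0.695) = 88% instead of 61%. The 20% rule removes AUCinf at the longer half-lives, though it leaves Cmax and AUC0-24 untouched.

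A correction is also imperfect. It borrows a level taken about three weeks earlier, and oral Kel rests on samples to 8 h plus the imputed 24 h value and may be unreportable. This is a good reason not to make corrected values the sole primary result, but not a reason to omit them.

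Finally, it is tempting to extend the point to the route comparison or the choice of dose. SAP 5.1 restricts the Bioavailability Population to multiple-dose IV or SC profiles, and SAP 5.7.3 places the SC-versus-oral comparison in Cohort 4, which has 15 days of SC dosing. The LDL-C and HDL-C endpoints do not use these data.

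**Conclusion.** The point holds, conditional on a quantifiable oral trough. As written, the plan reports oral-plus-SC exposure under the label of a single SC dose. Its direction follows from adding two positive concentrations under linear kinetics: Cmax, AUC0-24 and any reported AUCinf go up, CL/F goes down, and Kel and T1/2 describe a mixture. Its size remains open: negligible with a trough below quantification, and otherwise within the illustrative ranges above, which rest on one-compartment decline, a common elimination rate and the assumed half-lives and exposure ratios. The reach is limited to the descriptive single-dose SC summaries in Cohorts 1 to 3. This is worth correcting because the data needed are already collected, but it does not threaten the trial's main conclusions.

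**What to change.** Add to SAP 5.7.2, for each sub-study subject and each analyte:

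1. Report the single-dose SC parameters as measured, labelled as including residual oral drug.
2. Beside them, as a sensitivity analysis, report parameters computed after subtracting C24(oral) × exp(−Kel(oral) × t) from each post-SC concentration, with both quantities taken from that subject's Lead-in End profile. At time zero this removes the assigned value entirely. Set negative differences to zero. Where the subject's oral Kel is not reportable, use the cohort median.
3. Flag subjects whose C24(oral) exceeds a stated share of SC Cmax, fixed before the corrected results are seen. The documents give no basis for one value; the second table above shows what a given share implies.

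The correction scales itself: if C24 is zero, nothing changes. The cost is a few lines of PK programming and one extra set of columns, with no new samples. The downside is that the correction is approximate, since no Day 22 pre-dose sample is scheduled and the oral values predate 15 days of injections and an oral restart. That is why both sets should be shown.

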5.7.3 Relative Bioavailability Analysis

To compare the PK profile of atorvastatin and metabolites administered by the IV or SC route to that of oral administration, the relative bioavailability analysis will be performed for each cohort using key PK parameters (C_{max} , AUC_{0-24} and AUC_{inf}) of atorvastatin and, if data allow, its metabolites. Dose-normalized key PK parameters of the oral and IV (or SC) routes of administration will be log-transformed and analyzed using an analysis of variance (ANOVA) model including terms for treatment route as a fixed effect and subject as a random effect. The least squares geometric means ratio of atorvastatin oral vs IV (or SC) will be calculated. A 90% CI on the ratio of untransformed PK parameters will be derived through reverse transformation of the 90% CI for the difference in the log scale to the 90% CI for the ratio in the original scale.

When appropriate, the same analysis may be performed to compare the PK profile of the atorvastatin SC vs oral (Cohort 4).

The least-squares geometric means, ratio of the geometric means and 90% CIs on the ratio will be displayed.

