8.3.2 Investigational Medicinal Product (IMP) Preparation and Dosing Instructions

8.3.2.1 Intravenous Route

Atorvastatin injection is administered intravenously over 5 - 10 seconds into an antecubital or forearm vein. Following the Investigator's standard technique and equipment for preparing the injection site, the open-label study drug is administered without dilution. The dose is determined as directed in [Section 8.3.2.4](#). If any IV tubing is utilized, normal saline is used to flush the line immediately following the injection of IMP to clear the line of any residual drug and ensure complete dosing. The location of the injection is captured in the source documents, but not the CRF.

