9.3.4 Pharmacokinetic Assessments

Allowable time windows for PK draws are shown below in [Table 9-3](#). Sampling taken outside of the allowable windows still contribute to building the pharmacokinetic profile, but minor deviations are captured in the Case Report Form (CRF).

Blood samples are taken by either direct venipuncture or via an indwelling catheter; however, samples must not be taken from the same catheter or any device used for administering the study drug.

Pharmacokinetic blood samples are collected for analyzing atorvastatin and metabolite concentrations in plasma.

If blood samples are obtained from an indwelling catheter rather than direct venipuncture, the catheter must be kept patent with saline flushes. A blood sample of approximately 1 mL will be drawn and discarded prior to each saved collection.

The samples are frozen in a -20°C freezer within 120 minutes of being drawn.

The actual sample collection date and time is entered in the eCRFs. Any issues with the sampling process will be noted.

Table 9–3 Allowable Time Windows for Pharmacokinetic Draws

Route being studied	Target time of blood draw	Allowable time window
Oral (screening period)	Pre-dose	-60 to -1 minutes before a dose of oral atorvastatin is taken

	Hour 0.5	\pm 5 minutes
	Hours 1, 2, 4, 6, and 8	\pm 10 minutes
Intravenous or Subcutaneous (Day 15)	Prior to the IV or SC dose	-60 to -1 minutes before the dose of IV or SC atorvastatin is taken
	Immediately after the IV or SC dose	3 to 7 minutes following the end of the administration
	Hour 0.5	\pm 5 minutes
	Hours 1, 2, 4, 6, and 8	\pm 10 minutes
Subcutaneous (Day 22)	Hour 0.5	\pm 5 minutes
	Hours 1, 2, 4, 6, 8	\pm 10 minutes
	Hour 24	\pm 60 minutes

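### For parent atorvastatin, the oral:IV Cmax ratio in the relative bioavailability analysis does not measure bioavailability, and its IV term depends partly on when the 3-7 minute sample is drawn

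*SAP*

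**What the plan says.** SAP 5.7.3 gives its purpose as "To compare the PK profile of atorvastatin and metabolites administered by the IV or SC route to that of oral administration". The scale is stated as follows: "Dose-normalized key PK parameters of the oral and IV (or SC) routes of administration will be log-transformed". The model is an ANOVA in which subject is random and route is fixed. For the estimate, the SAP says: "The least squares geometric means ratio of atorvastatin oral vs IV (or SC) will be calculated", and a 90% CI accompanies it. On scope, it says that "the relative bioavailability analysis will be performed for each cohort using key PK parameters"; the three named are Cmax, AUC0-24 and AUCinf. All of them go through this one model, for parent drug and, where the data permit, for metabolites.

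Protocol 8.3.2.1 has the IV dose "administered intravenously over 5 - 10 seconds". Protocol 9.3.4, Table 9-3, allows the first post-dose IV sample "3 to 7 minutes following the end of the administration", and SAP 4.1.2 repeats the 3-7 minute window. Protocol 9.3.4 adds that out-of-window samples still contribute to the profile and that actual collection times go into the eCRF.

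SAP 5.7.2, Table 4, defines Cmax only as the highest plasma concentration. Neither document describes back-extrapolation to time zero or separate handling of Cmax after a bolus. SAP 5.7.2 asks for actual sampling times, yet it fixes the first post-bolus time at 0.0055 hour on the assumption of a 20-second bolus.

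**The concern.** In an oral-versus-oral or oral-versus-SC comparison, Cmax reflects the rate and extent of absorption, so its ratio belongs in a bioavailability table. After an IV bolus there is no absorption step. The parent concentration is highest at the end of the injection and is expected to fall from then on, so the largest observed value will normally be the first one drawn. That level is taken at an arbitrary early time, and the time may differ between subjects.

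At stake is how the PK tables are read. Protocol 5.4 says the PK profiles support the dosing regimen and the safety profile. A ratio with a 90% CI under a bioavailability heading would be read in that light. Its IV term and its interval would partly reflect draw timing, and the 0.0055 h assignment would present a 3-7 minute level as an end-of-bolus level.

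**Working it through.** **Inputs.** Injection duration is 5-10 s (Protocol 8.3.2.1), or 5/3600 to 10/3600 = 0.0014-0.0028 h. The first IV draw is at 3-7 min (Protocol Table 9-3, SAP 4.1.2), or 3/60 to 7/60 = 0.050-0.117 h. The SAP assigns 0.0055 h to it (SAP 5.7.2). The early half-life h is not in the documents; it is assumed here to lie between 2 and 120 min.

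**1. The plan's own figure.** 20 s / 3600 = 0.00556 h, so 0.0055 h (19.8 s) reproduces as a 20-second bolus. It matches neither the 5-10 s injection nor the draw window. The draw is 0.050/0.0055 = 9.1 to 0.1167/0.0055 = 21.2 times later than the assigned time.

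**2. What the ratio estimates.** Take the simplest model: one compartment, elimination rate k, volume V, steady state. Let F be oral bioavailability, T the oral peak time and t the first IV draw time. The steady-state accumulation factor is the same for both routes and cancels.
- Oral Cmax/dose is proportional to (F/V)·exp(−kT).
- The IV first-draw level/dose is proportional to (1/V)·exp(−kt).
- Ratio of Cmax values = F·exp(−k(T − t)).
- Ratio of AUC values = F.

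The Cmax ratio differs from F for any non-zero k unless T = t, and the draw time t appears in it. No half-life need be assumed to reach this.

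**3. Sensitivity to draw time.** With C(t) = C(0)·2^(−t/h), the 3- versus 7-minute factor is 2^(4/h), and the share of the end-of-injection level captured is 2^(−t/h). For h = 5: 2^(4/5) = 1.74, 2^(−7/5) = 0.38, 2^(−3/5) = 0.66.

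| Assumed h (min) | C(3)/C(7) | Share at 7 min | Share at 3 min |
|---|---|---|---|
| 2 | 4.00 | 9% | 35% |
| 5 | 1.74 | 38% | 66% |
| 10 | 1.32 | 62% | 81% |
| 30 | 1.10 | 85% | 93% |
| 60 | 1.05 | 92% | 97% |
| 120 | 1.02 | 96% | 98% |

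The oral:IV ratio moves inversely to the IV value. The first factor compares draws at opposite ends of the window.

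**4. Two-phase decline.** With C(t) = 0.8·2^(−t/h) + 0.2·2^(−t/240), where the weights and the slow half-life of 240 min are also assumptions, C(3)/C(7) is 1.804, 1.455, 1.232 and 1.078 for h = 2, 5, 10 and 30 min. The effect is smaller but follows the same pattern.

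**5. The 0.0055 h rule.** It leaves the Cmax value unchanged but misstates IV Tmax and the first AUC segment. Under the step 4 model, placing a 5-minute level at 0.33 min gives an area over the first 30 min of 0.33·C(5) + 29.67·(C(5) + C(30))/2. For h = 5, 10 and 30 the results are 11.96, 15.77 and 22.45, against true areas of 11.43, 15.85 and 23.06. The ratios are 1.05, 1.00 and 0.97. In this illustration the error is small, partly because two errors offset: the starting level is too low, and the linear trapezoid is too high over a convex decline.

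**The case against.** The strongest reply is that SAP 5.7.3 sets out to compare PK profiles, that Protocol 7 and SAP 3 list Cmax for that comparison, and that nothing is decided on the ratio. Doses are judged on LDL-C in eleven of thirteen subjects (SAP 5.6), and Protocol 12.3.2 adds HDL-C. No equivalence limits attach to the 90% CI. The ratio could simply be relabelled as observed early exposure. The point about consequence stands and limits how serious this is. Relabelling would cure the name but would leave a modelled ratio whose IV term moves with draw time.

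A reader might also infer more than the documents support:
- *That the IV sample misses the peak altogether.* This depends on an early half-life the documents do not give. At the slow end of the assumed range the sample is within about 4% of the end-of-injection level.
- *That draw time alone sets the IV value.* Dose, distribution volume and the subject also determine it.
- *That Cmax is unusable throughout.* Metabolites form after dosing and may peak later, within the 0.5-8 h samples. Cohort 4 (SC) has an absorption peak. The argument covers parent drug after IV dosing only.
- *That the replacement-dose decision or the safety assessment is compromised.* No criterion uses the ratio. Safety rests on adverse events, discontinuations, laboratory results and vital signs (SAP 5.8), and a dose-normalised ratio is no substitute for a peak-exposure comparison.

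**Conclusion.** The concern holds for parent atorvastatin, oral versus IV, in Cohorts 1-3. The Cmax ratio is not a bioavailability measure, because a bolus has no absorption phase. That conclusion needs no numerical assumption.

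The timing effect does need one. With a single-exponential early decline and half-lives of 2 to 120 minutes, a 3-minute draw gives about 4.0 to 1.02 times the value of a 7-minute draw, and 9% to 98% of the end-of-injection level is captured. The documents do not show where in that range the drug lies. It is further assumed that the parent level falls from the end of the injection, so that the first sample is the observed maximum.

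The consequence is confined to the reported PK comparison and its interpretation. It should be corrected in the SAP, but it does not threaten the efficacy conclusion.

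**What to change.** In SAP 5.7.3, for parent atorvastatin in Cohorts 1-3:
- Base oral-versus-IV relative bioavailability on AUC0-24, and on AUCinf where it is reportable under SAP 5.7.2. Remove Cmax from that modelled ratio.
- List and summarise the IV value as the first-sample concentration, with its actual draw time.

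Keep Cmax in the model for metabolites, shown with observed Tmax, and for oral versus SC in Cohort 4.

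In SAP 5.7.2, replace the 0.0055 h assignment with the recorded sampling time, in line with that section's own actual-times rule. The SAP should then also state how area before the first sample is obtained, since no rule is given. The 20-second assumption there and the 5-10 second injection in Protocol 8.3.2.1 need to be reconciled.

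The cost is SAP wording and one fewer modelled ratio in the IV tables. No new data are needed: draw times are already captured, and Cmax is still calculated and summarised as a listed endpoint.
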